5. STATISTICAL ANALYSES

Standard data derivation rules and stat methods are described in section 10.1 while the study specific data derivation rules and stat methods are described in section 9.

5.1. Analysis of demography and baseline characteristics

5.1.1. Analysis planned in the protocol

Demographic characteristics (age at vaccination in years, sex) will be summarized by group using descriptive statistics:

- Frequency tables will be generated for categorical variables such as sex.
- Mean, median, standard deviation and range will be provided for continuous data such as age.

The distribution of participants will be tabulated overall, per group and for each age category (60-69 years and 70-80 years).

Withdrawal status will be summarized by group using descriptive statistics:

- The number of participants enrolled into the study as well as the number of participants excluded from PP analyses will be tabulated.
- The numbers of withdrawn participants will be tabulated according to the reason for withdrawal.

5.1.2. Additional considerations

The analysis of demographic characteristics by group will be performed on the ES and on the PPS.

For a given participant and a given demographic variable, missing measurements will not be replaced.

Demography and baseline characteristics will also be summarized by country.

Vital signs (heart rate, respiratory rate, systolic/diastolic blood pressure) and pre-vaccination temperature reported at visit 1 will be summarized by group using descriptive statistics.

Participant disposition in the ES will be reported as a whole and per group, and for each age category (60-69 years and 70-80 years).

A summary of important protocol deviations leading to elimination will be provided by group.

The study population will also be summarized **for web disclosure** as follows:

- Percentage of enrolled participants by country will be tabulated by group,
- Percentage of enrolled participants by age categories (≤ 64 , 65-84, ≥ 85 YOA) will be tabulated by group.

5.2. Primary endpoint(s)

5.2.1. Analysis planned in the protocol

5.2.1.1. Safety analysis

The safety analysis will be performed on the ES for all participants.

A descriptive analysis by group and overall will present a summary of:

- The number and percentage of participants with at least one administration site event (solicited and unsolicited), with at least one systemic event (solicited and unsolicited) and with any AE during the 4-day or 30-day follow-up period will be tabulated with exact 95% CI after Dose 3. The same computations will be done for Grade 3 AEs, Grade 3 non-serious AEs, related AEs and AEs resulting in a medically attended visit.
- The number and percentage of participants reporting each individual solicited administration site event (any grade, Grade 3, with medically attended visit) and solicited systemic event (any grade, Grade 3, with medically attended visit) during the 4-day follow-up period (i.e., on the day of vaccination and 3 subsequent days) will be tabulated for each group after Dose 3.
- For fever, the number and percentage of participants reporting fever by half degree ($^{\circ}\text{C}$) cumulative increments during the 4-day follow-up period (i.e., on the day of vaccination and 3 subsequent days) will be tabulated for each group after Dose 3.
- The number and percentage of participants with any unsolicited AEs during the 30-day follow-up period (i.e., on the day of vaccination and 29 subsequent days) with its exact 95% CI will be tabulated by group and by Medical Dictionary for Regulatory Activities (MedDRA) preferred term. The same tabulation will be done for Grade 3 unsolicited AEs, for any causally related unsolicited AEs, for Grade 3 causally related unsolicited AEs and for unsolicited AEs resulting in a medically attended visit. The verbatim reports of unsolicited AEs will be reviewed by a qualified person and the signs and symptoms will be coded according to the MedDRA Dictionary for Adverse Reaction Terminology. Every verbatim term will be matched with the appropriate Preferred Term.
- The number and percentage of participants with at least one report of SAE/pIMD classified by the MedDRA Preferred Terms and reported during the 30-day follow-up period (i.e., on the day of vaccination and 29 subsequent days) will be tabulated with exact 95% CI. The same tabulation will be done for related SAEs/pIMDs. SAEs/pIMDs will also be described in detail.

- The number and percentage of participants using concomitant medication (any medication, any antipyretic and any antipyretic taken prophylactically, respectively) during the 4-day follow-up period (i.e., on the day of vaccination and 3 subsequent days) and during the 30-day follow-up period (i.e., on the day of vaccination and 29 subsequent days) will be summarized by group.

5.2.1.2. Humoral immune response up to 1 month post-Dose 3

The analysis for immunogenicity will be performed on the PPS for the 120-AS01E_B group only.

At each time point that blood samples are collected for humoral immune response and for each assay (unless otherwise specified), the analyses below will be performed:

- Percentage of participants with antibody titers/concentrations above the positivity cut-off and their exact 95% CI will be tabulated.
- GMTs/GMCs and their 95% CI will be tabulated and represented graphically.
- Antibody titers/concentrations will be displayed using reverse cumulative curves.
- The mean geometric increase (MGI) i.e. geometric mean of ratios of antibody titers/concentrations of each post-vaccination time point over pre-vaccination, will be tabulated with 95% CI.
- Individual post-vaccination results versus pre-vaccination results will be plotted using scatter plots.
- Distribution of the fold increase of the antibody titers/concentrations (post- over pre-vaccination titers/concentrations) will be tabulated.
- The ratio of fold increase (pre to post) of anti-RSVPreF3-specific antibody concentrations over the fold increase (pre to post) of anti-RSV-A neutralizing antibody titers will be tabulated using descriptive statistics and displayed graphically using scatter plots.
- The fold increase of post-dose 3 (in RSV OA=ADJ-011 EXT:002 MTH20 study) over post-dose 1 (in RSV OA=ADJ-002 study) antibody titers/concentrations will be tabulated using descriptive statistics.

Pre-vaccination will be both pre-Dose 1 in RSV OA=ADJ-002 and pre-Dose 3 in RSV OA=ADJ-011 EXT:002 MTH20.

The immunogenicity analysis will also be performed by age category (60-69 years and 70-80 years, age according to the parent study).

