6.5. Concomitant therapy

At each study visit/contact, the investigator or delegate should question the participant about any medications/products taken and vaccinations received by the participant.

The following concomitant medication(s)/product(s)/vaccine(s) must be recorded in the eCRF:

- All concomitant medications/products/vaccines, except vitamins and dietary supplements, administered during the 30-day period following vaccination (Day 1 to Day 31).
- Any concomitant medications/products/vaccines leading to study participation/intervention non-eligibility, or an elimination from the analysis (refer to Section 5.2.2 for details).
- Any prophylactic medication (e.g. analgesics, antipyretics) administered on the day of study vaccination (Day 1) and in the absence of ANY symptom and in anticipation of a reaction to the vaccination.
- Any concomitant medications/products/vaccines relevant to an SAE/pIMD to be reported as per protocol or administered at any time during the study period for the treatment of an SAE/pIMD. Concomitant medications relevant to SAEs and pIMDs must be recorded on the Expedited Adverse Event Report.
- *Shingrix* or any AS01-containing vaccine throughout the entire study.

CONFIDENTIAL213569 (RSV OA=ADJ-011 EXT:002 MTH20)
Protocol Amendment 1 Final

The Local Medical Lead (LML) should be contacted if there are any questions regarding concomitant or prior therapy.

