- The number and percentage of participants with any unsolicited AEs during the 30-day follow-up period (i.e., on the day of vaccination and 29 subsequent days) with its exact 95% CI will be tabulated by group and by Medical Dictionary for Regulatory Activities (MedDRA) preferred term. The same tabulation will be done for Grade 3 unsolicited AEs, for any causally related unsolicited AEs, for Grade 3 causally related unsolicited AEs and for unsolicited AEs resulting in a medically attended visit. The verbatim reports of unsolicited AEs will be reviewed by a qualified person and the signs and symptoms will be coded according to the MedDRA Dictionary for Adverse Reaction Terminology. Every verbatim term will be matched with the appropriate Preferred Term.
- The number and percentage of participants with at least one report of SAE/pIMD classified by the MedDRA Preferred Terms and reported during the 30-day follow-up period (i.e., on the day of vaccination and 29 subsequent days) will be tabulated with exact 95% CI. The same tabulation will be done for related SAEs/pIMDs.
- The number and percentage of participants using concomitant medication (any medication, any antipyretic and any antipyretic taken prophylactically, respectively) during the 4-day follow-up period (i.e., on the day of vaccination and 3 subsequent days) and during the 30-day follow-up period (i.e., on the day of vaccination and 29 subsequent days) will be summarized by group.

CONFIDENTIAL213569 (RSV OA=ADJ-011 EXT:002 MTH20)
Protocol Amendment 1 Final**9.4.3.2. Humoral immune response up to 1 month post-Dose 3**

At each time point that blood samples are collected for humoral immune response and for each assay (unless otherwise specified), the analyses below will be performed:

- Percentage of participants with antibody titers/concentrations above the positivity cut-off and their exact 95% CI will be tabulated.
- GMTs/GMCs and their 95% CI will be tabulated and represented graphically. Antibody titers/concentrations will be displayed using reverse cumulative curves.
- Distributions of antibody titers/concentrations will be tabulated.
- The mean geometric increase (MGI) i.e. geometric mean of ratios of antibody titers/concentrations of each post-vaccination time point over pre-vaccination, will be tabulated with 95% CI.
- Individual post-vaccination results versus pre-vaccination results will be plotted using scatter plots.

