10.3.7.1. Time period for collecting and recording AEs, SAEs, and pIMDs

All AEs that occur during 30 days following administration of the dose of study vaccine (Day 1 to Day 31) must be recorded into the appropriate section of the eCRF, irrespective of intensity or whether or not they are considered vaccination-related.

CONFIDENTIAL213569 (RSV OA=ADJ-011 EXT:002 MTH20)
Protocol Amendment 1 Final**10.3.7.2. Follow-up of AEs, SAEs, pIMDs**

After the initial AE/SAE/pIMD or any other event of interest for the study, the investigator is required to proactively follow each participant at subsequent visits/contacts. All SAEs and non-serious AEs of special interest as defined in the Section [10.3.5.1](#), will be followed until the event is resolved, stabilized, otherwise explained, or the participant is lost to follow-up.

Other non-serious AEs must be followed until 30 days after the last vaccination or until the participant is lost to follow-up.

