2. OBJECTIVES/ENDPOINTS

Objectives	Endpoints
Primary	

 To evaluate the safety and reactogenicity following intramuscular (IM) administration of RSVPreF3 OA investigational vaccine up to 1 month post-Dose 3, for all participants. 	
 Occurrence of solicited adverse events (AEs) up to 4 days post-Dose 3 (Day 4). Occurrence of unsolicited AEs up to 30 days post-Dose 3 (Day 31). Occurrence of serious adverse events (SAEs)/ Potential immune mediated diseases (pIMDs) up to 30 days post-Dose 3 (Day 31).

 To evaluate the humoral immune response following IM administration of RSVPreF3 OA investigational vaccine up to 1 month post-Dose 3, for participants vaccinated with 2 doses of RSVPreF3 OA investigational vaccine in the parent study. 	
 Humoral immune response at 1 month post-Dose 3 (Day 31) in terms of: 
 Neutralizing antibody titers against Respiratory Syncytial Virus (RSV)-A Neutralizing antibody titers against RSV-B
Secondary	

 To evaluate the humoral and cell-mediated immune (CMI) response following IM administration of RSVPreF3 OA investigational vaccine up to 1 month post-Dose 3, for participants vaccinated with 2 doses of RSVPreF3 OA investigational vaccine in the parent study. 	
 Humoral immune response at 1 month post-Dose 3 (Day 31) in terms of: 
 RSVPreF3-specific Immunoglobulin G (IgG) antibody concentrations CMI response at 1 month post-Dose 3: 
 Frequency of RSVPreF3-specific CD4+ T-cells identified as expressing at least 2 markers among IL-2, CD40L, TNF-α, IFN-γ

 To evaluate the safety and reactogenicity following IM administration of RSVPreF3 OA investigational vaccine up to the study end, for all participants. 	
 Occurrence of SAEs from vaccination (Day 1) up to study end (Month 6). Occurrence of pIMDs from vaccination (Day 1) up to study end (Month 6).
Tertiary	

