2040	Administration of any medication forbidden by the protocol 
Any investigational or non-registered medication or medical device used during the study period beginning 30 days before the dose of study vaccineImmunosuppressants or other immune-modifying drugs administered chronically (i.e., more than 14 consecutive days in total) during the period starting 90 days prior to the vaccine doseLong-acting immune-modifying drugs administered at any time during the study periodImmunoglobulins and/or any blood products or plasma derivatives administered during the period starting 90 days before the dose of study vaccine	Day 1, Day 31	PPS for analysis of immunogenicity

CONFIDENTIAL

213569 (RSV OA=ADJ-011 EXT:002 MTH20)

Statistical Analysis Plan Amendment 1

Code	Condition under which the code is used	Visit (timepoints) where the code is applicable	Applicable for analysis
2060	
Intercurrent medical condition
 
 Participants may be eliminated from the PPS for immunogenicity if, during the study, they incur a condition that has the capability of altering their immune response (intercurrent medical condition) or are confirmed to have an alteration of their initial immune status (other than RSV infection) 	Day 1, Day 31	PPS for analysis of immunogenicity
2080	
Participants did not comply with dosing schedule
 
 Number of days between dose 2 in the parent study RSV OA=ADJ-002 and dose 3 in current study is outside [510-570 days] 	Day 1	PPS for analysis of immunogenicity
2090	
Participants did not comply with blood sample schedule
 
 Number of days between vaccination at Day 1 and Day 31 blood sample is outside [30-42 days] 	Day 31	PPS for analysis of immunogenicity
2100	
Serological results not available post-dose
 
 No immunological result at visit 2 for all the following tests: RSV A/B Neutralizing antibody titer, RSVPref3-specific IgG antibody concentration and RSVPref3-specific CD4+ T cells frequency 	Day 31	PPS for analysis of immunogenicity
2120	
Obvious incoherence or abnormality or error in data
 
 Unreliable released data as a result of confirmed sample mismatch or confirmed inappropriate sample handling at laboratory 	Day 1, 31	PPS for analysis of immunogenicity

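### The primary unsolicited AE and SAE/pIMD endpoints run to Day 31, but their tables stop at Day 30

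*SAP*

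**What the plan says.** The primary safety endpoints in SAP section 2, identical in Protocol Table 3, include "Occurrence of unsolicited AEs up to 30 days post-Dose 3 (Day 31"), and the SAE/pIMD endpoint has the same limit. Recording follows that limit. Protocol 10.3.7.1 covers "All AEs that occur during 30 days following administration of the dose of study vaccine (Day 1 to Day 31"), and Protocol 6.5 requires concomitant medication "administered during the 30-day period following vaccination (Day 1 to Day 31").

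The analysis sections use a shorter window. SAP 5.2.1.1 describes the unsolicited AE table as covering the "30-day follow-up period (i.e., on the day of vaccination and 29 subsequent days) with its exact 95% CI will be tabulated by group". Protocol 9.4.3.1 gives the same rule and applies it to SAEs/pIMDs: "reported during the 30-day follow-up period (i.e., on the day of vaccination and 29 subsequent days"). Concomitant medication in SAP 5.2.1.1 is handled likewise, "during the 30-day follow-up period (i.e., on the day of vaccination and 29 subsequent days) will be summarized by group". The Schedule of Activities (Protocol 1.3) also gives Days 1-30 for recording unsolicited AEs, so the protocol states the recording window in two ways. SAP section 8 lists no change from the protocol analysis.

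**The concern.** The declared primary endpoint and the table meant to report it cover different periods. A programmer who follows the written counting rule leaves out events that the endpoint includes and that sites are required to record.

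What happens to a Day 31 event depends on its type:

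- An SAE or pIMD is missing from the primary 30-day table but counted in the whole-study tables of SAP 5.3.1.3.
- Any other unsolicited AE appears at most in listings, or in summaries with no stated window (SAP 5.2.2.1.3 and 5.5).
- Concomitant medication started that day is recorded but falls outside its 30-day summary.

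Safety is the first stated purpose of the study, so the primary safety tables should cover the period that the endpoint names.

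**Working it through.** **Day numbering.** Visit 1 and vaccination are Day 1, so study day = date − dose date + 1. Protocol Table 2 puts Visit 2 (Day 31) at an interval of 30 days. SAP 4.2.2.1, code 2090, agrees, excluding a participant if the "Number of days between vaccination at Day 1 and Day 31 blood sample is outside [30-42 days"]. Day 31 is therefore dose date + 30.

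**The plan's own figures.**

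| Item | Source | Last day |
|---|---|---|
| Unsolicited AE and SAE/pIMD endpoints | Protocol Table 3, SAP 2 | dose + 30 = Day 31 |
| AE recording | Protocol 10.3.7.1 | Day 31 |
| Concomitant medication recording | Protocol 6.5 | Day 31 |
| Unsolicited AE recording | Protocol 1.3 | Day 30 |
| Primary tables | Protocol 9.4.3.1, SAP 5.2.1.1 | dose + 29 = Day 30 |
| Solicited endpoint | SAP 2 | Day 4 |
| Solicited tables | SAP 5.2.1.1 | dose + 3 = Day 4 |

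Each 30-day figure is correct as a day count: vaccination day plus 29 is 30 days, and 30 days after the dose is Day 31. They are different windows, and the difference is Day 31. The solicited pair agrees, so the mismatch is confined to the 30-day tables.

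**Placement of events.** SAP 5.2.2.1.2 selects unsolicited AEs by onset day. SAP 10.1.3.5 calls onset day the number of days between dose and start, then sets it to 1 on the dose day. With that anchor, a Day 31 event has onset day 31 and is out. As a plain date difference it would be 30, which a programmer could let in. The rule is ambiguous, but it does not override the explicit limit of 29 days after vaccination.

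**Size.** The share of the endpoint window left out is 1/31 = 3.2%. The documents give no AE incidence. Assume a proportion p31 of participants with an unsolicited AE by Day 31, and a constant hazard. Then p30 = 1 − (1 − p31)^(30/31). For example, at p31 = 0.20, p30 = 1 − 0.80^(30/31) = 0.1942. Half-widths are for exact (Clopper-Pearson) 95% intervals at p31.

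| p31 | p30 | Shortfall (points) | Per 300 | Per 100 | Half-width, n=300 | Half-width, n=100 |
|---|---|---|---|---|---|---|
| 0.20 | 0.1942 | 0.58 | 1.73 | 0.58 | 4.7 | 8.3 |
| 0.30 | 0.2919 | 0.81 | 2.43 | 0.81 | 5.3 | 9.4 |
| 0.40 | 0.3900 | 1.00 | 2.99 | 1.00 | 5.7 | 10.0 |
| 0.50 | 0.4887 | 1.13 | 3.39 | 1.13 | 5.8 | 10.2 |

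As a lower bound, a 5% incidence by Day 30 gives p31 − p30 = 1 − 0.95^(31/30) − 0.05 = 0.16 points, about 0.5 of 300. For a rare event at an assumed 1% by Day 31, the shortfall is 0.03 points, about 0.1 of 300. If a rare event does fall on Day 31, it shows: 0/100 (95% CI 0 to 3.62%) becomes 1/100 (0.03 to 5.45%), and 0/300 (0 to 1.22%) becomes 1/300 (0.01 to 1.84%).

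**The case against.** The strongest reply is that Day 31 is only the name of Visit 2. The same tag marks the humoral endpoints, where it means the visit, and code 2090 accepts a Day 31 sample taken 30 to 42 days after vaccination. The solicited endpoint adds weight: "Occurrence of solicited adverse events (AEs) up to 4 days post-Dose 3 (Day 4") counts the vaccination day as the first day, and by that convention 30 days would end on Day 30, as the tables do. On this view the Day 31 tag is the outlier.

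This does not remove the conflict. Protocol 10.3.7.1 and 6.5 use Day 31 as the end of a recording range that starts on Day 1, which a visit label cannot explain. The 4-day convention and the Schedule of Activities show only that the documents state the window in two ways.

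Several other points stand:

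- The effect is small, its size rests on assumed incidences, and it would be smaller if onsets cluster early.
- The same rule applies to all three groups, and the study has no hypothesis test.
- Ending at Day 30 has a practical merit. Visit 2 may fall on Day 31 itself, so that day may be only partly observed, whereas Days 1-30 are complete for anyone seen within the visit window.
- Relabelling the endpoint and recording windows to Day 30 would also give consistency, but it would change a declared primary endpoint.

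**Conclusion.** The inconsistency is real, and nothing in either document reconciles it. Following the written rule drops Day 31 from the primary tables. The practical loss is non-serious, non-pIMD AEs starting on that day, because SAEs and pIMDs return in the Month 6 tables.

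On the assumed 20-50% incidence and constant hazard, the understatement is about 0.6-1.1 participants per group of about 100, small against the interval half-widths. It is smaller still in the combined rows for any AE, where participants with a solicited event are already counted. Power and error rates are untouched. This should be corrected so that the tables report the stated endpoint, but it does not threaten the study's conclusions.

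**What to change.** Use one last day for endpoint, recording and analysis in both documents. To keep the declared endpoint, define the window in SAP 5.2.1.1 and Protocol 9.4.3.1 as the vaccination day plus the next 30 days (Day 1 to Day 31). Apply it to unsolicited AEs, SAEs/pIMDs and concomitant medication, and align the Schedule of Activities.

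Two optional clarifications would help: write onset day in SAP 10.1.3.5 as start date − dose date + 1, and state the same window for the combined summary in SAP 5.2.2.1.3.

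The cost is wording and one programming parameter, since Protocol 10.3.7.1 and 6.5 already require the data. Reported percentages may rise slightly. The 30-day label should become Day 1 to Day 31, with a note that Day 31 may be partly observed for participants whose Visit 2 falls on it.

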5.2.2. Additional considerations

5.2.2.1. Safety analysis

5.2.2.1.1. Solicited Events

Solicited events will be reported daily during the 4-day (from Day 1 to Day 4) follow up period after vaccination, using structured diaries. Missing or non-evaluable measurements will not be replaced. Therefore, the analysis of solicited events will include only vaccinated participants with documented solicited safety data (i.e., paper diary completed).

In order to summarize the data, the maximum intensity of local injection site erythema/swelling (in mm) and fever (in °C) will be categorized as follows:

Grading	Erythema/swelling	Fever
0:	≤ 20 mm	< 38.0°C (100.4°F)
1:	> 20 - ≤ 50 mm	≥ 38.0°C (100.4°F) - ≤ 38.5°C (101.3°F)
2:	> 50 - ≤ 100 mm	> 38.5°C (101.3°F) - ≤ 39.0°C (102.2°F)
3:	> 100 mm	> 39.0°C (102.2°F)

Fever is defined as temperature ≥ 38.0°C / 100.4°F (regardless of the location of measurement). The preferred location for measuring temperature in this study will be the oral cavity. Body temperature will also be summarized by 0.5°C increments as follows: ≥38.0, >38.5, >39.0, >39.5, >40.0 °C.

Each participant’s data will be summarized according to the maximal severity observed during the follow-up period for each event, followed by a summary across participants.

- Compliance in completing solicited events information will be tabulated.
- The number of days with solicited events reported during the 4-day follow-up period will be tabulated for each solicited event, using descriptive statistics (mean, min, Q1, median, Q3, maximum). The same tabulation will be done for Grade 3 solicited events.
- The prevalence of each solicited event (any grade and grade 3) will also be represented graphically per group.

